1.2 Measures/Instruments

O3 will be produced through the ACT-5000 Ozonetech corona discharge generator, (Mellifiq, Sweden), and mixed with room air in a sealed 3m x 3m x 2m chamber. O₃ will be delivered to subjects via a tube connected to the inspiratory valve on a three-way non-rebreathe mouthpiece. The Thermo ScientificTM 49iQ Ozone Analyzer (Franklin, MA, USA) will be attached to the inspiratory tube and used as an O3 sensor. Calibration will occur according to the manufacturing standards using the Thermo ScientificTM 49iQ Ozone Primary Standard generator.

Spirometry will be measured through the ParvoMedics OUS-SPIRO on the metabolic cart (Salt Lake City, UT, USA), which will be calibrated prior to each use. While wearing a nose-clip, participants will be asked to complete a maximal inspiration to maximal lung capacity followed by a maximal forceful exhalation for 6-seconds, following breathing out at the end of a normal breath. This will allow for measurement of forced expiratory volume in one-second (FEV1), forced vital capacity (FVC), forced mid-expiratory flow (FEF₂₅₋₇₅), and peak expiratory flow rate (PEFR). Based on guidelines provided by the American Thoracic Society (ATS), trials will be repeated a minimum of 3 times until the two largest FEV1 and FVC values differ by less than or equal to 150mL (Graham et al., 2019). Spirometry values will be compared between the two experimental trials to examine how O₃ exposure may impact development of expiratory flow limitation.

Fractional nitric oxide concentration in expired breath (FeNO) will be measured by a calibrated 2nd generation NOBreathe® FeNO monitor (Bedfont® Scientific Ltd., England). Participants will be instructed to perform a deep inhalation away from the mouthpiece, and exhale at a consistent flow rate for 12 seconds into the mouthpiece of the device until prompted to stop by the monitor. Four measurements will be taken at each specified time point. FeNO will be compared between the two experimental trials to examine how O₃ exposure may impact lung inflammation.

Symptoms will be measured via a custom brief questionnaire previously used in the laboratory. Before and after each exercise bout, participants will be asked to rate symptoms related to their eyes, nose, throat, chest, and general health on a 0-5 scale, where 0 means "you

Page 5 of 23

don't experience this symptom at all" and 5 means "very severe". Symptoms will be compared between the two experimental trials to examine how O₃ exposure may impact symptom development.

Dyspnea during rest and exercise will be measured using a modified Borg scale (Gaber et al., 2019). During rest and exercise, participants will be asked "How strong/intense is your breathing discomfort?" in which zero will represent "no breathing discomfort" and 10 represent "the most severe breathing discomfort that you have ever experienced or could imagine experiencing." Ratings of dyspnea will be compared between the two experimental trials to examine how O₃ exposure may impact dyspnea.

Rating of perceived exertion (RPE) during exercise will be measured using the Borg scale (Borg, 1982). Participants will be intermittently asked to express how hard they feel like they are working, on a scale from 6 to 20, where a 6 represents "no exertion" and a 20 represents "maximal exertion." Ratings of perceived exertion will be compared between the two experimental trials to examine how O₃ exposure may impact RPE, as well as assess each subject's state during the graded exercise test.

Blood lactate will be measured via testing strips and a portable LactatEDGE analyzer (Warsaw, Poland) by sampling at the finger tip of the index or middle finger. The skin surface will be prepared by cleaning with an alcohol swab, wiping with gauze, followed by puncturing the skin with a lancet. After wiping the first drop of blood, the second drop will be analyzed for concentration of blood lactate (mmol/L). The discarded lancet will be placed in a designated sharps bin, while any other materials exposed to blood (gauze, alcohol swab, discarded strips) will be placed in the marked biohazard bin. A trained researcher wearing gloves will obtain all samples. Blood lactate values will be utilized to determine aerobic and anaerobic thresholds

Page 6 of 23

during the step-incremental cycling test, as well as compared between the two experimental trials to examine how O₃ exposure may impact production of lactate.

Inspiratory capacity maneuvers will be performed during rest and exercise to assess ventilatory patterns. While connected to the mouthpiece, participants will be asked to fill up their lungs completely from the end of a normal expiration. The volume of air inspired during these tasks will represent the inspiratory capacity of the subject, and will be compared between the two experimental trials to examine how O₃ exposure may impact dynamic hyperinflation of the lungs during exercise.

1.3 Study Design

This research design can be characterized as a double-blind crossover with pre- and postmeasures. Ozone pollution status is the independent variable, of which there are two levels during the experimental trials: ozone exposure at 170 parts per billion (ppb) O3, and room air (<10 ppb O3). Testing will take place over four laboratory sessions, with a minimum of 72 hours of washout between each visit. During the first session, subjects will undergo a step-incremental test on a cycle ergometer to determine subject characteristics and identify anaerobic threshold, followed by familiarization of exercise pulmonary function tests. During the second visit, subjects will undergo resting spirometry and assessment of exhaled nitric oxide before and after exposure to 120 minutes of O₃ at 750ppb to characterize resting response. The third and fourth laboratory visits will consist of 30-minutes of cycling at the workload associated with 10% below previously established anaerobic threshold with exposure to either ozone or room air. Post-exercise spirometry and FeNO measures will be obtained prior to a time to exhaustion test at 105% of previously established peak power output. During the O₃ condition, subjects will be exposed to 170ppb for 60 minutes prior to, and during the cycling tasks, whereas during the control condition subjects will breathe room air for the identical procedures. Both the primary researcher and subjects will be blinded to the experimental condition for each visit, with the order randomized for each subject.

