1.4 Procedures

Participants will visit the laboratory for testing on 4 occasions. A minimum of 72-hours washout is required between visits. Before each session involving exercise (Visits 1,3,4), subjects will be asked to prepare as if each visit was a competition or important training session in their training schedule, and to ensure preparation is as similar as possible prior to each visit to minimize variability in results. This will include, but is not limited to, avoiding alcohol and strenuous exercise for 24 hours, ensuring a proper sleep the night prior, and consuming a pre-exercise meal that they are accustomed to timed appropriately prior to each visit. However, participants will be advised not to consume any ergogenic aids (i.e., sodium bicarbonate) or stimulants (i.e., significant doses of caffeine) for 24 hours prior to each visit, even if they typically utilize such strategies during competition. All visits involving exercise (Visits 1,3,4) will be performed at a similar time of day in order to avoid any diurnal variation in exercise performance (Kusumoto et al., 2021).

The first visit will involve participant consent, screening for inclusion based on a maximal exercise test, and familiarization with pulmonary function measurements. Participants will first re-read the consent form. They will be given the opportunity to ask any questions related to their involvement, then be asked to sign the informed consent. Participants will also complete a PAR-Q+ form, which will be reviewed prior to partaking any exercise in the laboratory. Participants will then be familiarized with pulmonary function testing equipment and protocols, and undergo resting spirometry and FeNO measurements (described in detail above).

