The second visit will consist of resting exposure to ozone and pulmonary function tests. Subjects will conduct pre-ozone resting spirometry, FeNO, dyspnea, and symptom measurements, followed by 2-hours of resting O₃ exposure at 750ppb. During the resting exposure, subjects will be seated with a three-way non-rebreathe valve and mouthpiece connected via tube to the ozone chamber. Nose-clips will be worn for the entirety of the protocol, and expired volumes will be analyzed to determine average minute ventilation, and effective dose of O3 (minute ventilation x O₃ concentration x exposure duration) (Silverman et al., 1976). Subjects will be permitted to use personal electronic devices (phone, laptop, tablet etc.) during exposure, provided no significant movement is required. Following exposure, subjects will complete identical spirometry, FeNO, symptoms, and dyspnea measurements immediately and 30-minutes post-exposure to that completed pre-exposure. Post-exposure and pre-exposure values will be compared to determine resting response to O3.

The third and fourth visits will consist of identical procedures, randomized as to the order of the O3 and control conditions. During both experimental trials, a lab member other than the researcher will control the O₃ concentration in order to maintain blinding of the participant and the researcher as to the condition. During the O₃ exposure, subjects will receive 170ppb O₃, and during the control exposure subjects will receive room air (typically <10ppb O₃). Upon arrival in the laboratory, the researcher will confirm that pre-visit requirements (detailed above) are met, prior to resting spirometry, FeNO, symptoms, and dyspnea measurements. Subjects will then be connected via tube and mouthpiece/valve to the O₃ chamber. While remaining connected to the O₃ chamber, participants will then complete a standardized warmup on the Velotron of 25-

Page 10 of 23

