1.5 Data Analysis

As the purpose of this research study is to assess the interaction between O₃ exposure and cardiorespiratory function during rest and exercise in healthy athletes, we aim to characterise the relationship between resting response and exercise response, as well as assess the effects of ozone exposure on pulmonary function, ventilatory patterns and exercise parameters. To assess susceptibility to exercising O₃ response, a regression analysis will occur between the reduction in spirometry values post 2-hours resting exposure at 750ppb and the reduction in spirometry values post-O₃ condition exercise trial. It is hypothesized that greater decrements in FEV1, FVC, FEF₂₅₋₇₅ and PEFR will occur following exercise under O₃ exposure in subjects who also exhibited greater expiratory flow limitations following resting exposure.

Page 11 of 23

Examining ventilatory patterns during exercise is another primary objective of the proposed research study. By comparing tidal volume, breathing frequency, and inspiratory capacity throughout the constant work-rate exercise bout between the two experimental conditions through mixed models, further insight into how O₃ exposure may impact ventilation may be gained.

Analyzing time to exhaustion (in seconds) for the maximal constant work-rate exercise bouts between the two experimental conditions will also be assessed by mixed models. Potential differences between the two conditions will help elucidate whether performance changes occur due to O₃ exposure. Further analysis of ratings of perceived exertion, dyspnea, and FeNO via mixed models will also occur between the two experimental trials.

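### The 72-hour washout is unsupported and never checked; the stated analysis names no period term or same-visit baseline, so ozone carried from Visit 3 into an air Visit 4 would bias the contrast unseen

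*Combined protocol and SAP*

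**What the plan says.** Sections 1.3 and 1.4 apply one minimum interval to every gap between visits: "with a minimum of 72 hours of washout between each visit" and "A minimum of 72-hours washout is required between visits". Neither gives a source, a rationale, a maximum or a recovery criterion.

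Visit 2 always comes before the two randomised visits. Spirometry and FeNO are taken there "before and after exposure to 120 minutes of O₃ at 750ppb to characterize resting response", and its follow-up measurements are made "immediately and 30-minutes post-exposure to that completed pre-exposure". Nothing later at Visit 2 shows how recovery proceeds. In the ozone condition at Visit 3 or 4, "subjects will be exposed to 170ppb for 60 minutes prior to, and during the cycling tasks". The order is randomised for each subject; no blocking or balance of sequences is stated.

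Pre-exposure values are collected throughout. At Visit 1, before any ozone, participants "undergo resting spirometry and FeNO measurements". Visit 2 adds pre-ozone dyspnea and symptoms. At Visits 3 and 4 the researcher confirms the pre-visit requirements "prior to resting spirometry, FeNO, symptoms, and dyspnea measurements".

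Section 1.5 uses pre-exposure values only implicitly, to form the spirometry reductions for the regression. For the other outcomes it says: "Further analysis of ratings of perceived exertion, dyspnea, and FeNO via mixed models will also occur between the two experimental trials". The terms of the mixed models are not listed.

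**The concern.** A two-period crossover relies on each person starting both periods in the same state, apart from a shift that the model can absorb. Here the preceding exposure differs by visit (Visit 3 always follows 750 ppb) and, at Visit 4, by sequence (after 170 ppb with exercise, or after room air). The plan itself accepts that FeNO can carry an earlier insult: section 1.1 excludes anyone with an upper respiratory infection in the previous 4 weeks for that reason.

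If recovery were incomplete, the plan as written would neither show it nor protect the contrast. A small or null ozone effect on FeNO, symptoms, dyspnea or spirometry could not then be told apart from an air visit contaminated by the ozone visit before it. The data needed to look are already being collected.

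**Working it through.** **Plan's own figure.** The 15 subjects in section 1.1 reproduce with a paired F-test (0.95 L, SD 0.86 L, zero within-person correlation, two-sided 0.05): power 0.803. This point does not depend on that figure. N = 24 is used below.

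**Notation (assumed, additive).** R is the residual from Visit 2 present at Visit 3. L is the residual present at Visit 4 after an ozone Visit 3. The documents size neither. For one person, the contribution to ozone minus air is:
- ozone first: R − L
- air first: −R

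**Path 1, Visit 2 into Visit 3 (L = 0).**
- With a period term, the estimate is the mean of the two sequence means: (R − R)/2 = 0 for any split.
- Without one, bias = R × (n ozone-first − n air-first)/24: 0 at 12:12, 4/24 = 0.17R at 14:10, 8/24 = 0.33R at 16:8.
- Under simple randomisation, exact 12:12 has probability 0.16. The mean absolute bias is 0.16R, and the chance that it reaches R/6 is 0.54. The expected bias is zero.
- At 12:12 without a period term, the standard error is multiplied by √(1 + R²), with R in SDs of the within-person difference: 1.03, 1.12 and 1.41 for R = 0.25, 0.5 and 1.0.

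**Path 2, ozone Visit 3 into air Visit 4.** With a period term, bias = ((R − L) − R)/2 = −L/2. At 12:12 it is the same without the term. For an assumed L of 0.10 log units this is −0.05.

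**What baseline adjustment buys.** Assume log FeNO with day-to-day SD d = 0.12 (shared by pre and post values within a visit) and measurement SD m = 0.08. For Visit 3 − Visit 4 differences:
- post-value variance: 2(0.0144 + 0.0064) = 0.0416
- covariance of pre and post differences: 2(0.0144) = 0.0288, so slope b = 0.0288/0.0416 = 0.69
- variance after adjustment: 0.0416 × (1 − 0.69²) ≈ 0.0217
- variance of the pre-to-post change: 4(0.0064) = 0.0256
- cost of estimating the covariate (21 residual df): √(1 + 1/20) = 1.025

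Standard-error ratio, covariate model against post-only: √(0.0217/0.0416) × 1.025 = 0.74, a 26% reduction. Against the change contrast: √(0.0217/0.0256) × 1.025 = 0.94, a 6% reduction. Both arise with no carry-over at all.

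The same formulas over a range of assumed d/m, with the share of the Path 2 bias that the covariate leaves (1 − b):

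| d/m | b | SE vs post-only | SE vs change | Path 2 bias left |
|---|---|---|---|---|
| 0.5 | 0.20 | 1.00 | 0.79 | 80% |
| 1.0 | 0.50 | 0.89 | 0.89 | 50% |
| 1.5 (case above) | 0.69 | 0.74 | 0.94 | 31% |
| 2.0 | 0.80 | 0.61 | 0.97 | 20% |

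At d/m = 1.5 and L = 0.10, the covariate leaves 0.31 × (−0.05) ≈ −0.015. The change contrast leaves 0, provided the residual passes in full from the pre to the post value. A simulation with 12:12 sequences gave −0.049 (post-only), −0.015 (covariate) and 0.000 (change).

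**What a recovery check can show.** A paired comparison of pre-exposure values with n = 24 has 80% power only for shifts of about 0.60 SD of the paired difference; the 95% CI half-width is 2.069/√24 = 0.42 SD. Path 2 needs a comparison between sequences, 12 against 12, where the half-width is 2.074 × √(2/12) = 0.85 SD.

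**The case against.** The strongest reply is that the worrying exposure, 750 ppb at Visit 2, cannot bias the comparison systematically, because it precedes both randomised orders. That stands. A reader might infer that residual 750 ppb effect at Visit 3 biases the ozone-air contrast. The documents do not support this: such a residual is a period effect with zero expected bias. It matters as noise, through chance imbalance if no period term is fitted, or if it changes the response to the next exposure, which cannot be judged from the documents.

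Second, section 1.3 describes a design with pre- and post-measures, and section 1.5 does not list its model terms, so the mixed models may already contrast pre with post. This also stands. A reader might infer that adjustment is worth 1.8 or more times the sample size (1/0.74² = 1.8). That figure needs a post-value-only comparator and the assumed SDs, and it appears without any carry-over, so it does not measure the harm from a short washout. Against a pre-post contrast the gain is about 6%.

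Third, nothing shows that a residual exists at 72 hours. Agreed: this is an unverified assumption, not a demonstrated bias.

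What the reply does not answer is Path 2, which a period term leaves untouched, or the absence of any stated use of the pre-exposure values to examine recovery.

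**Conclusion.** The concern holds in a limited form. The 72-hour interval is unsupported, no analysis checks it, and section 1.5 states neither a period term nor a same-visit baseline for FeNO and dyspnea. Visit 2 residual costs precision and, without a period term, a chance shift averaging 0.16R under simple randomisation. Carry-over from an ozone Visit 3 to an air Visit 4 would move the contrast by half the residual, toward hiding an ozone effect when the residual has the same sign as the effect.

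These results assume additive residuals that persist from pre to post value within a visit; the SDs and residual sizes are assumptions. It is worth correcting because the remedy is cheap, not because a bias has been shown. Confidence is medium.

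**What to change.** In section 1.5:

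1. Fit a period term. In the FeNO, dyspnea, symptom and spirometry models, include each person's same-visit pre-exposure value as the within-person Visit 3 − Visit 4 difference. Give the pre-to-post change contrast as a sensitivity analysis, because measurement error in the baseline means that the covariate only partly removes Visit 3-to-4 carry-over.
2. Report pre-exposure values at Visits 3 and 4, by sequence, against Visit 1 for spirometry and FeNO and against Visit 2 pre-exposure for symptoms and dyspnea. Give estimates with 95% confidence intervals, and state that a null result at n = 24 does not prove washout.
3. Do not exclude visits on their pre-exposure value. At Visit 4 that value follows the randomised Visit 3 exposure, so exclusion would select on something treatment may have changed, and it would break pairs.

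The cost is wording and about one or two degrees of freedom per model; no new visits, measurements or participants are needed. The length of the interval is for the sponsor to justify.

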minutes at 10% below previously established aerobic threshold. Subjects will then be provided with 5-minutes of rest prior to completing 30-minutes at 10% below anaerobic threshold. Expired gas and volumes will be analyzed throughout the trial, and participants will perform an inspiratory capacity test, have blood lactate sampled via finger-prick, rate their perceived exertion and dyspnea every 10-minutes (10,20,30-minutes into exercise). Post-exercise, subjects will remove their mouthpiece and complete spirometry, FeNO, dyspnea, and symptoms testing (~5mins), prior to reattaching the mouthpiece and completing a time-to-exhaustion test at 105% of peak power achieved during the GXT. Strong verbal encouragement will be provided to subjects, and exercise will be stopped when they are no longer able to maintain 60 RPM, and time-to-exhaustion will be recorded. Post-exercise, a final set of pulmonary function, symptoms, and dyspnea testing will occur at 30-minutes following completion of the submaximal exercise bout.

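### Do Sections 1.3 and 1.4 prescribe different lengths of ozone exposure at Visits 3 and 4?

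*Combined protocol and SAP*

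**What the plan says.** Section 1.3 (Study Design) describes the experimental visits in outline: "The third and fourth laboratory visits will consist of 30-minutes of cycling at the workload associated with 10% below previously established anaerobic threshold", followed by post-exercise measures and a time-to-exhaustion test. For the ozone condition it adds that "subjects will be exposed to 170ppb for 60 minutes prior to, and during the cycling tasks". It mentions neither a warm-up nor a rest interval.

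Section 1.4 (Procedures) gives the sequence. After baseline measures, "Subjects will then be connected via tube and mouthpiece/valve to the" ozone chamber. Still connected, "participants will then complete a standardized warmup on the Velotron of 25" minutes, at a work rate set from the aerobic threshold. "Subjects will then be provided with 5-minutes of rest prior to completing 30-minutes at 10% below anaerobic threshold". Afterwards "subjects will remove their mouthpiece and complete spirometry, FeNO, dyspnea, and symptoms testing (~5mins), prior to reattaching the mouthpiece" for the exhaustion test. Section 1.4 states no total exposure time and no interval between connection and the start of the warm-up.

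Both sections say that the room-air visit follows the same procedures as the ozone visit. Effective dose is defined in Section 1.4 as minute ventilation times ozone "concentration x exposure duration", in the paragraph on Visit 2 only.

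**The concern.** The comma in the Section 1.3 sentence invites the reading of an hour of ozone first, then ozone during cycling. A reader who takes it that way finds no such hour in Section 1.4. The length of exposure, which is part of the treatment definition, would then appear to be 60, 90 or 120 minutes.

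Duration is one of the three factors in the plan's dose formula, and Section 1.1 justifies the fitness criterion partly as a way to give participants a similar effective dose. If different schedules were run for different participants, the ozone effect would vary between them for a reason unrelated to susceptibility. That would add noise to the exercise response that the Section 1.5 regression tries to explain. A different schedule on a participant's two visits would undermine the crossover comparison itself.

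**Working it through.** **Plan's own figure.** Section 1.3 gives 60 minutes. The Section 1.4 steps up to the end of the constant-load bout are warm-up 25, rest 5 and bout 30: 25 + 5 + 30 = 60 minutes. The figure is reproduced if it denotes the whole period.

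**Other readings of Section 1.3** (minutes before the exhaustion test)
- An hour before the 30-minute bout, then the bout: 60 + 30 = 90.
- An hour before the warm-up, then the full Section 1.4 sequence: 60 + 25 + 5 + 30 = 120.

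At 170 ppb, concentration times time is 170 × 60 = 10,200, 170 × 90 = 15,300 and 170 × 120 = 20,400 ppb·min. The three totals come from how one sentence in Section 1.3 is read. Section 1.4 does not list a pre-exposure, but it does not exclude one either, because the time from connection to warm-up is left open.

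**Effect on inhaled dose.** The documents give no ventilation values, so these are assumptions: rest 8 to 15 L/min, warm-up 50 to 80 L/min, bout 80 to 120 L/min, and the 5-minute interval at twice the resting value. The extra time is taken as seated rest. Concentration is constant and cancels, so:

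relative increase = (extra minutes × resting ventilation) / (25 × warm-up + 5 × interval + 30 × bout)

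| Rest / warm-up / bout (L/min) | Volume over 60 min (L) | 60 extra min | 30 extra min |
|---|---|---|---|
| 8 / 80 / 120 | 2,000 + 80 + 3,600 = 5,680 | 480/5,680 = 8.5% | 240/5,680 = 4.2% |
| 10 / 70 / 100 | 1,750 + 100 + 3,000 = 4,850 | 600/4,850 = 12.4% | 300/4,850 = 6.2% |
| 10 / 60 / 100 | 1,500 + 100 + 3,000 = 4,600 | 600/4,600 = 13.0% | 300/4,600 = 6.5% |
| 15 / 60 / 80 | 1,500 + 150 + 2,400 = 4,050 | 900/4,050 = 22.2% | 450/4,050 = 11.1% |
| 15 / 50 / 80 | 1,250 + 150 + 2,400 = 3,800 | 900/3,800 = 23.7% | 450/3,800 = 11.8% |

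The first and last rows are the extremes of the assumed ranges. Doubling the minutes therefore adds about 8% to 24% to the dose, because resting ventilation is small beside exercise ventilation.

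**Effect on the planned analyses (Section 1.5).**
- The mixed models compare ozone with room air within participants. With the same schedule on both visits, any length of exposure gives a fair comparison at that exposure.
- The regression relates the fall in spirometry after exercise in ozone to the fall after resting exposure. Dose enters neither side. A common change of schedule would alter the size of the exercise response being predicted, not the validity of the analysis.
- No Visit 3 or 4 analysis uses effective dose. Expired gas and volumes are analysed throughout these visits, so the ventilation needed to describe the dose afterwards will be available.

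**The case for a change.** The best case for a change is that the reading that reconciles the sections fits Section 1.3 imperfectly. That section speaks of cycling tasks in the plural and describes two, the constant-load bout and the exhaustion test. The Section 1.4 steps use up 60 minutes before the second task begins, so 60 minutes cannot be the total across both. It has to end with the first bout, or denote the hour leading up to the exhaustion test, and Section 1.3 says neither. Someone other than the blinded researcher controls the ozone and needs one schedule to work from.

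The criticism of the wording stands. The consequence does not. The operator and the researcher cannot run even one experimental visit without agreeing when the participant is connected and when the warm-up starts, and the requirement of identical procedures carries that schedule to the other visit.

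One could also set the exercise dose against the Visit 2 dose. With 10 L/min at rest, Visit 2 gives 750 × 120 × 10 = 900,000 ppb·L. With 60 and 100 L/min in exercise, Visit 3 or 4 gives 170 × 4,600 = 782,000 for the 60-minute sequence and 782,000 + 170 × 60 × 10 = 884,000 with an extra hour, ratios of 0.87 and 0.98. The plan makes no such comparison, so the shift affects no planned result.

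**Conclusion.** The Section 1.3 sentence is ambiguous. On one reading it matches the 60 minutes in Section 1.4; on others it implies 90 or 120 minutes, which Section 1.4 neither lists nor rules out. This is a gap in written detail that the laboratory fills in setting up the visits, not a flaw in the design or the analysis. The difference in inhaled dose between the 60- and 120-minute readings is about 8% to 24%, a range that rests wholly on assumed ventilation and on the extra hour being seated rest.

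The conclusion assumes that one schedule is used for every participant and on both visits. The plan requires identical procedures across conditions; uniformity across participants is the ordinary expectation for a single protocol run in one laboratory. On that basis the ozone versus room-air comparison is unbiased and the regression remains sound. Which duration is intended is for the investigators to say.
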